5.3.7 Secondary Efficacy Analyses

Key Secondary Efficacy Analyses

The following key secondary efficacy endpoints are considered confirmatory endpoints and will therefore be part of the testing procedure in order to control for multiplicity as described in section 5.4.

Absolute change from baseline in 6 minute walking distance and in SGRQ total score after 24-weeks treatment

6 minute walking distance (6MWD)

The 6 minute walking distance (6MWD) is captured as part of the 6 minute walk test (6MWT) (See general description of 6MWT under Further Secondary Efficacy Analyses). Absolute change from baseline in 6 minute walking distance, will be summarized by treatment group and visit. The key secondary endpoint, absolute change from baseline after 24 weeks of treatment, will be analysed as described below.

St Georges Respiratory Questionnaire (SGRQ)

The St Georges Respiratory Questionnaire (SGRQ) is a respiratory specific questionnaire. The symptoms component with 3-month symptoms recall is used. The three domain scores, Symptoms, Activity, and Impacts and the Total score will be calculated. Scores are expressed as a percentage of overall impairment where 100 represents worst possible health status and 0 indicates best possible health status. The standard scoring algorithms will be applied, as described in the St George's Respiratory Questionnaire Manual Version 2.3, June 2009.

The three derived domain scores and total score, and the corresponding changes from baseline will be summarised by treatment group and visit. Individual item responses will only be listed. The key secondary efficacy endpoint, Change from baseline in SGRQ total score after 24-weeks of treatment will be analysed as described below.

Analysis of change from baseline after 24 weeks of treatment in 6 minute walking distance (6MWD) and Total SGRQ

Absolute change from baseline in 6MWD and in SGRQ will be analyzed using the same ANCOVA model as for (A-a)DO₂, including all data irrespective of adherence to treatment regimens as the main approach, and the results from these analyses will be part of the procedures to control for multiple testing (see section 5.4).

Sensitivity analyses for absolute change from baseline in 6MWD and SGRQ will be done using similar approaches as those used for the sensitivity analyses for (A-a)DO₂, but will be limited to:

- Mixed model for repeated measurements (MMRM),
- ANCOVA after multiple imputation,
- ANCOVA completer analysis
- ANCOVA based on the per protocol set (PPS).

Mean profiles for 6MWD and SGRQ over time will be provided.

Time to WLL during 24-weeks treatment

Kaplan-Meier plots will be used to assess time to WLL (time from randomisation to documentation of fulfilment of criterion for requiring WLL) and treatment comparisons corresponding to those made for primary endpoint, will be analysed by a logrank test adjusting for the randomisation strata (WLL). Subjects who fulfil the criteria for rescue treatment (i.e., worsening of aPAP based on symptoms, reduced exercise capacity and/or findings of hypoxemia or desaturation according to the Investigator's judgement), will be counted as if WLL was conducted at the date of fulfilment of rescue treatment criteria. In this analysis, subjects withdrawing from the trial will be handled as censored at time of discontinuation, and subjects who reach week 24 and have not needed WLL will be censored at time point for Visit at week 24. Survival estimates for time to WLL will be tabulated for subjects in each group who require WLL, by relevant time points, along with 95% Cis.

Sensitivity analyses for time to WLL will be carried out as follows:

- Any subject withdrawing from trial before week 24 and before fulfilling criteria for WLL will be handled as having WLL the day after discontinuation date. This is done to

evaluate the impact of missing data and censoring due to withdrawals. The same analyses as planned above will be conducted in order to evaluate the robustness of results with regards to the handling of censoring.

- A Cox regression will be applied where the hazard ratio and its 95% confidence interval will be estimated, while including adjustment for treatment, Japan vs other countries and WLL (stratification). The analysis will be done using the same approach for handling censoring as done in the main analysis.

Further Secondary Efficacy Analyses

The further secondary efficacy endpoints will be statistically analysed, although the analyses will be considered supportive rather than confirmatory, and will therefore not be part of the testing procedures implemented for primary and key secondary efficacy endpoints to control for multiplicity.

All data will be tabulated using summary statistics including levels at each visit and change from baseline for continuous data, and counts and shifts including percentage of subjects within categories for frequency data. Tables will be based on all observed data applicable to the FAS population.

Number of WLLs over time

A Generalized Linear Model, based on the negative binomial distribution, is planned for analysis using the number of WLLs as the dependent variable and will include treatment group and the stratification factor of whether or not a WLL was conducted within 2 months prior to the Baseline (according to protocol version 4.0 and later versions), or whether or not WLL was conducted between the screening visit and the randomization visit (according to protocol versions before version 4.0), and country (Japan vs. all others) as fixed effects. The analysis will be adjusted for each subject's length of follow-up in the trial. The rate ratio (each active dose group: placebo) will be derived from the model along with the 95% 2-sided Confidence Intervals. Model adjusted mean rates for each treatment group will be derived. In this analysis each lung lavaged contributes as an event in the count per subject, regardless of whether both lungs are lavaged on different days or on the same day. Events with the date of criteria met in the double-blind period will be counted as being conducted in the double-blind period.

6 minute walking test (6MWT)

Each item related to the six minutes walk test (6MWT) will be summarized by visit. Summaries will include distance and duration of walk during the test, the pre and post walk Borg CR10, the derived change in dyspnoea score (post walk Borg CR10 score – pre walk Borg CR10 score), the SpO₂ at start and the worst SpO₂ during the walk, blood oxygen desaturation derived as (SpO₂ at start – Worst SpO₂ during the walk). Change from baseline after 24 weeks of treatment in; blood oxygen desaturation, difference in pre- to post-test dyspnoea score and distance and duration of walk will in addition be summarized separately including categorical variables corresponding to improved tolerance to exercise (derived as increase in distance walked ≥50 m (compared to baseline) or desaturation <4 percentage points on the 6MWT, respectively), see below.

CT scan

CT scans will be centrally evaluated by two independent and blinded assessors at the 24 weeks treatment visit where change in relation to the baseline assessment will be graded as: *Improved, Worsened, No change, Data missing or Impossible to evaluate*. This evaluation, as well as the Ground-Glass Opacification (GGO) score for each anatomical area (upper, middle and lower), (graded as: *no GGO, less than 5%, 5-24%, 25-49%, 50-74%, 75% or more GGO*) will be summarized in frequency tables by treatment group including proportion

of subjects reaching each grade. The number of subjects with, and without, improvements will be analyzed (see, below).

Continuous endpoints

The following continuous endpoints will be analysed using the same main model (ANCOVA) as applied for primary endpoint, including all collected data irrespective of adherence to treatment regimens.

- Absolute change in VC (% predicted), haemoglobin corrected DLCO (% predicted), FEV₁ (% predicted), and FVC (% predicted), and relative change in PaO₂ from baseline after 24 weeks of treatment.
- Change from baseline in pre and post-exercise dyspnoea scores and cough scores (severity and frequency VAS scores) after 24-weeks treatment.

Categorical Endpoints

Number of subjects classified as having improvements in parameters, as defined below, will be summarised by visit in frequency tables, including cumulative counts. Logistic regression models will be applied to statistically analyse if proportion of subjects having improvements differ between treatment groups according to the same groups as applied for analyses of primary and key secondary endpoints. The logistic regressions will include the same covariates as for main analysis of primary endpoint, although with the baseline covariates corresponding to each respective endpoint. The complement in these analyses, subjects not reaching improvements according to the categorisations, will be based on the total number of subjects applicable to the FAS population.

- Number of subjects with >5 mmHg/>0.67 kPa and number of subjects with >10 mmHg/>1.33 kPa improvement in (A-a)DO₂ after 24-weeks treatment
- Number of subjects with >5 percentage points and number of subjects with >10 percentage points improvement in VC (% predicted) after 24-weeks treatment
- Number of subjects with >10 percentage points improvement in DLCO (% predicted) after 24-weeks treatment
- Number of subjects with >10 percentage points improvement in FEV₁ (% predicted) after 24-weeks treatment
- Number of subjects with >10 percentage points improvement in FVC (% predicted) after 24-weeks treatment
- Number of subjects with >10% relative improvement in PaO₂ after 24-weeks treatment
- Number of subjects with improved tolerance to exercise (increase in distance walked ≥50 m or desaturation <4 percentage points on the 6MWT) compared to baseline after 24-weeks treatment
- Number of subjects with improved CT score after 24-weeks treatment

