10.2.2.1 Key Secondary Endpoints

- Change from baseline in 6MWD after 24-weeks treatment
- Change from baseline in SGRQ total score after 24-weeks treatment
- Time to WLL during 24-weeks treatment
- Number of AEs, SAEs, ADRs, severe AEs and AEs leading to treatment discontinuation, including clinically significant changes in laboratory tests and electrocardiographic (ECG) variables, during 24-weeks treatment

10.2.2.2 Further Secondary Endpoints:

- Absolute change from baseline in VC (% predicted), DLCO (% predicted), FEV₁ (% predicted) and FVC (% predicted), and relative change from baseline in PaO₂ after 24-weeks treatment
- Number of subjects with >5 mmHg/>0.67 kPa and number of subjects with >10 mmHg/>1.33 kPa improvement in (A-a)DO₂ after 24-weeks treatment
- Number of subjects with >5 percentage points and number of subjects with >10 percentage points improvement in VC (% predicted) after 24-weeks treatment
- Number of subjects with >10 percentage points improvement in DLCO (% predicted) after 24-weeks treatment
- Number of subjects with >10 percentage points improvement in FEV₁ (% predicted), FVC (% predicted) after 24-weeks treatment
- Number of subjects with >10% relative improvement in PaO₂ after 24-weeks treatment
- Number of subjects with improved tolerance to exercise (increase in distance walked ≥50 m or desaturation <4 percentage points on the 6MWT) after 24-weeks treatment
- Change from baseline in dyspnoea score and cough scores after 24-weeks treatment

- Number of subjects with improved CT score after 24-weeks treatment

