12.1.7 Further Secondary Efficacy Analyses

Analyses of further secondary endpoints will be described in the SAP.

The following tabulations will be presented:

- Number of subjects with >5 mmHg/>0.67 kPa and number of subjects with >10 mmHg/>1.33 kPa improvement in (A-a)DO₂ after 24-weeks treatment
- Number of subjects with >5 percentage points and number of subjects with >10 percentage points improvement in VC (% predicted) after after 24-weeks treatment
- Number of subjects with >10 percentage points improvement in DLCO (% predicted) after 24-weeks treatment
- Number of subjects with >10 percentage points improvement in FEV₁ (% predicted) and FVC (% predicted) after 24-weeks treatment
- Number of subjects with >10% relative improvement in PaO₂ after 24-weeks treatment
- Number of subjects with improved tolerance to exercise (increase in distance walked ≥50 m or desaturation <4 percentage points on the 6MWT) after 24-weeks treatment
- Number of subjects with improved CT score after 24-weeks treatment

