5.3.8 Exploratory Efficacy Analyses

Exploratory secondary efficacy endpoints will only be summarised descriptively by visit and treatment group unless otherwise specified below.

Double-blind treatment period

Absolute change from baseline in Blood Gas and Lung Function Tests

Absolute change from baseline of (A-a)DO₂, VC (% predicted), DLCO (% predicted), FEV₁ (% predicted), FVC (% predicted), and relative change from baseline of PaO₂ after 4 and 12-weeks treatment will be summarised by visit according to description in previous sections.

Time period during which the (A-a)DO₂ level is maintained below Baseline minus 10mmHg

This time period will be defined as the difference between the date of the visit where the (A-a)DO₂ level first reaches below the baseline level minus 10 mmHg and the date of the first visit where the where the (A-a)DO₂ level first reaches above the baseline level minus 10mmHg. For subjects never reaching the first threshold before ending the double-blind treatment period, the time period will be set to zero, and for subjects never reaching the second threshold, the time period will be set to the duration between the visit where the first threshold it reached and the last visit of the double-blind treatment period. This time period, in days, will be summarised descriptively.

Number of subjects with improved tolerance to exercise

Number of subjects with improved tolerance to exercise (increase in distance walked ≥ 50 m (compared to baseline) or desaturation < 4 percentage points on the 6MWT, respectively) after 4 and 12-weeks treatment will be summarised by visit according to description in previous sections.

Time period during which the improvement in tolerance to exercise is maintained

The time period during which the improvement in tolerance to exercise is maintained will be defined as the difference between the date of the visit where subjects are for the first time classified as having improvement in tolerance to exercise, defined as increase in distance walked ≥ 50 m (compared to baseline), and the date of the first visit where the increase in distance walked is above ≥ 50 m compared to baseline on the 6MWT. This time period, in days, will be summarised descriptively.

Dyspnoea score and cough scores

Change from baseline in dyspnoea score and cough scores (severity and frequency) after 4 and 12-weeks treatment will be summarised as described in previous sections for 24 weeks of treatment.

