Table	14.2.3.20	Analysis of number of subjects with >5 percentage points improvement in VC (% predicted) compared to baseline after 24 weeks treatment (Logistic regression)		X					
Table	14.2.3.21	Number and % of subjects with >10 percentage points improvement in VC (% predicted) compared to baseline by visit during 24 weeks treatment		X					
Table	14.2.3.22	Analysis of number of subjects with >10 percentage points improvement in VC (% predicted) compared to baseline after 24 weeks treatment (Logistic regression)		X					
Table	14.2.3.23	Number and % of subjects with >10 percentage points improvement in DLCO (% predicted) compared to baseline by visit during 24 weeks treatment		X					
Table	14.2.3.24	Analysis of number of subjects with >10 percentage points improvement in DLCO (% predicted) compared to baseline after 24 weeks treatment (Logistic regression)		X					
Table	14.2.3.25	Number and % of subjects with >10 percentage points improvement in FEV1(% predicted) compared to baseline by visit during 24 weeks treatment		X					
Table	14.2.3.26	Analysis of number of subjects with >10 percentage points improvement in FEV1(% predicted) compared to baseline after 24 weeks treatment (Logistic regression)		X					
Table	14.2.3.27	Number and % of subjects with >10 percentage points improvement in FVC (% predicted) compared to baseline by visit during 24 weeks treatment		X					
Table	14.2.3.28	Analysis of number of subjects with >10 percentage points improvement in FVC (% predicted) compared to baseline after 24 weeks treatment (Logistic regression)		X					
Table	14.2.3.29	Number and % of subjects with >10% relative improvement in PaO2 compared to baseline by visit during 24 weeks treatment		X					
Table	14.2.3.30	Analysis of number of subjects with >10% relative improvement in PaO2 compared to baseline after 24 weeks treatment (Logistic regression)		X					
Table	14.2.3.31	Summary of change from baseline in SpO2 at start and the worst SpO2 oxygen desaturation and distance of walk during 6 minutes walk test (6MWT) by visit during 24 weeks treatment		X					

			SCR	DB-FAS	DB-PPS	DB-SAF	FU-FAS	FU-MOL INT	FU-SAF
Table	14.2.3.32	Number of subjects with improved tolerance to exercise (increase from baseline in distance walked ≥ 50 m) by visit during 24 weeks treatment		X					
Table	14.2.3.33	Analysis of number of subjects with improved tolerance to exercise (increase from baseline in distance walked ≥ 50 m) after 24 weeks treatment (Logistic regression)		X					

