Table	14.2.3.34	Number of subjects with improved tolerance to exercise (desaturation < 4 percentage points on the 6MWT) by visit during 24 weeks treatment full analysis set		X					
Table	14.2.3.35	Analysis of number of subjects with improved tolerance to exercise (desaturation < 4 percentage points on the 6MWT) after 24 weeks treatment (Logistic regression)		X					
Table	14.2.3.36	Summary of Borg CR10 pre post and corresponding difference in walk dyspnea score and change from baseline in scores by visit during 24 weeks treatment		X					
Table	14.2.3.37	Analysis of change from baseline in dyspnea score after 24 weeks (ANCOVA)		X					
Table	14.2.3.38	Summary of cough (VAS) scores and change from baseline in cough scores by visit during 24 weeks treatment		X					
Table	14.2.3.39	Analysis of change from baseline in cough (VAS) scores after 24 weeks (ANCOVA)		X					
Table	14.2.3.40	Summary of number of subjects with Improved Worsened or No change in CT score during 24 weeks of treatment		X					
Table	14.2.3.41	Summary of CT Ground-Glass Opacification (GGO) score during 24 weeks of treatment		X					
Table	14.2.3.42	Analysis of number of subjects with Improved CT score compared to baseline after 24 weeks treatment (Logistic regression)		X					
Table	14.2.3.43	Summary of number of WLLs over time		X					
Table	14.2.3.44	Summary of details related to WLLs including reasons for, one or both lungs, and saline volume used.		X					
Table	14.2.3.45	Analysis of number of WLLs over time (negative binomial regression)		X					
Exploratory Efficacy Endpoints Double-Blind Treatment Period									
Table	14.2.4.1	Summary of time during which the (A-a)DO ₂ level is maintained below baseline (A-a)DO ₂ level -10 mmHg		X					
Table	14.2.4.2	Summary of time period during which the improvement in tolerance to exercise is maintained		X					
Table	14.2.4.3	Summary of SGRQ dimension scores and corresponding changes from baseline by visit during 24 weeks of treatment		X					
Table	14.2.4.4	Summary of number of subject with improved QoL score (improvement of at least 4 units on SGRQ total score) during 24 weeks of treatment		X					
Table	14.2.4.5	Summary of EQ-5D-5L dimension scores and corresponding shifts from baseline by visit during 24 weeks of treatment		X					
Table	14.2.4.6	Summary of Krebs von den Lungen-6 (KL-6) and change from baseline in Krebs von den Lungen-6 (KL-6) by visit during 24 weeks of treatment		X					

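### The SAP treats the exercise-tolerance responder as one either-limb composite in some places and as two separate responders in others, and no listed output reports the composite

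*SAP*

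**What the plan says.** Four places describe a single responder.

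- Protocol 10.2.2.2 lists one endpoint: "Number of subjects with improved tolerance to exercise (increase in distance walked ≥50 m or desaturation <4 percentage points on the 6MWT".
- Protocol 12.1.7 plans one tabulation in the same terms: "increase in distance walked ≥50 m or desaturation <4 percentage points on the 6MWT".
- SAP 2.2 keeps it as one bullet.
- SAP 5.3.7, Categorical Endpoints, says that "Logistic regression models will be applied to statistically analyse if proportion of subjects having improvements differ between treatment groups". Its list has this endpoint as one entry: "increase in distance walked ≥50 m or desaturation <4 percentage points on the 6MWT) compared to baseline after 24-weeks treatment".

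Three places describe two responders.

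- SAP 5.3.7, in the 6MWT paragraph, speaks of categorical variables in the plural, "derived as increase in distance walked ≥50 m (compared to baseline) or desaturation <4 percentage points on the 6MWT, respectively".
- SAP 5.3.8 uses the same form for Weeks 4 and 12, "increase in distance walked ≥ 50 m (compared to baseline) or desaturation < 4 percentage points on the 6MWT, respectively", and again in its follow-up list.
- SAP Appendix 1 gives each limb its own by-visit count (Tables 14.2.3.32 and 14.2.3.34) and its own model. Table 14.2.3.33 is "Analysis of number of subjects with improved tolerance to exercise (increase from baseline in distance walked ≥ 50 m) after 24 weeks treatment (Logistic regression" and Table 14.2.3.35 is "Analysis of number of subjects with improved tolerance to exercise (desaturation < 4 percentage points on the 6MWT) after 24 weeks treatment (Logistic regression". Follow-up Tables 14.2.5.12 and 14.2.5.13 are divided in the same way.

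SAP 5.1 lists four changes from the protocol. A split of this endpoint is not among them.

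**The concern.** A programmer working from the table list would produce two responder rates and two p-values for each dose comparison, all under the name of improved exercise tolerance. None would be the rate of the either-limb responder that the protocol defines. A programmer working from the Categorical Endpoints list would fit a model that has no table to go into. If this is settled only after unblinding, the limb with the better result could be quoted under the endpoint's name.

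**Working it through.** **1. Is this only loose wording?** Three features suggest that the SAP holds two definitions.

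- The word at the end of the 6MWT derivation assigns one criterion to each of several variables. The Categorical Endpoints list has no such word.
- Where SAP 2.2 separates measures that share a protocol bullet, it writes separate bullets: FEV₁ and FVC, and SGRQ and EQ-5D-5L. It left this endpoint whole.
- SAP 5.3.8 also defines the duration of improved exercise tolerance on distance alone, so the label is used in a third sense.

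**2. Can the composite be read off the component tables?** Let pA be the proportion meeting the distance limb and pB the proportion meeting the desaturation limb. Then

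max(pA, pB) ≤ P(A or B) ≤ min(1, pA + pB).

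The documents give no component rates, so these are assumed:

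- 20% and 30%: composite between 30% and 50%.
- 30% and 30%: between 30% and 60%.
- 40% and 50%: between 50% and 90%.

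The position within each range depends on how many subjects meet both limbs, which the component tables do not show. The composite has to be derived per subject.

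**3. What happens to the arm difference?** The only relevant figure in the documents is the blinded 6MWD residual MSE of 4928.203 in SAP Appendix 2. Its square root is 70.2 m, as stated there. It is a residual SD adjusted for baseline and stratum and pooled over the arms. Using it as the SD of change, with normal changes, is an assumption.

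P(gain ≥50 m) = 1 − Φ((50 − m)/70.2)

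- Mean change m = 0: 1 − Φ(0.712) = 24%.
- Mean change m = 50: 1 − Φ(0) = 50%.
- Difference on the distance limb: 26 points.

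Now assume that the limbs are independent and that a proportion q meets the desaturation limb, with q between 20% and 40%. The composite is 1 − (1 − p)(1 − q), where p is the distance-limb rate (0.238 at m = 0, 0.50 at m = 50).

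- q = 20% in both arms: 1 − 0.762 × 0.8 = 39% and 1 − 0.5 × 0.8 = 60%; difference 21 points.
- q = 40% in both arms: 1 − 0.762 × 0.6 = 54% and 1 − 0.5 × 0.6 = 70%; difference 16 points.
- q = 20% on placebo and 40% on active: 39% and 70%; difference 31 points.

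The composite difference can therefore be smaller or larger than the 26 points of the distance limb, depending on a treatment effect on desaturation that the documents do not state.

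**The case against.** The strongest reply is that the composite is not lost. SAP 5.3.7 prescribes logistic regression for the endpoints in its Categorical Endpoints list, the composite is on that list, and the 6MWT paragraph points forward to it. This stands. A reader who sees only the table list might infer that the defined endpoint is never analysed, and the SAP text does not support that. What remains is that the text and the table list disagree and that no listed output carries the composite.

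Protocol 12.1.7 also leaves the analysis of further secondary endpoints to the SAP, and the SAP does specify the component regressions. It would therefore be wrong to call them unplanned. The protocol elsewhere puts separate measures in one bullet, so a component reading is conceivable. It fits poorly here, because the word joining the limbs is kept in both SAP 2.2 and the Categorical Endpoints list.

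A reader might also infer that splitting the endpoint flatters the treatment, since the arm difference falls from 26 to 16–21 points when the composite is used. That holds only if the desaturation rate is equal in both arms. The third case in the working reverses the direction.

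Finally, each table title states its criterion and both limbs are to be reported, so quoting only one would be visible. This lowers the risk but does not say which result is the endpoint.

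**Conclusion.** The point holds as an internal contradiction in the SAP: one responder in SAP 2.2 and the Categorical Endpoints list, two in the 6MWT paragraph, SAP 5.3.8 and Appendix 1. No composite output is listed and no change is declared. This rests on comparing the texts and needs no numerical assumption.

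The composite rate lies between the larger component rate and the sum of the two, so the planned tables cannot supply it. The effect on the arm difference is unknown in size and direction, and the figures in the working only illustrate this.

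The consequence is minor. SAP 5.3.7 treats further secondary analyses as supportive and outside the multiplicity procedure. Walk distance is tested separately as a continuous key secondary endpoint. No confirmatory error rate is affected.

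**What to change.** - Add one by-visit frequency table and one Week 24 logistic regression for the per-subject composite as defined in Protocol 10.2.2.2.
- Name the baseline covariates. SAP 5.3.7 calls for the baseline matching each endpoint, and a two-limb responder has no single match. Use baseline 6MWD and baseline desaturation, with treatment, WLL stratum and Japan versus other countries as already planned. Baseline desaturation matters because Protocol 10.2.2.2 words that limb as a level, not as a change.
- Retitle Tables 14.2.3.32 to 14.2.3.35 and 14.2.5.12 to 14.2.5.13 as the two components of the responder. The component regressions can stay as supportive analyses.
- Align the 6MWT paragraph of SAP 5.3.7, and the Week 4, Week 12 and follow-up entries of SAP 5.3.8, with SAP 2.2 and the Categorical Endpoints list.
- If two separate endpoints are intended, record and justify that in SAP 5.1 before unblinding.

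The cost is one extra table and one extra model from 6MWT data already collected, plus retitling.
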